8.3 Subject Population(s) for Analysis

- All-completed population: All subjects that receive at least one dose will be considered for analysis.

9 Safety and Adverse Events

9.1 Definitions

Unanticipated Problems Involving Risk to Subjects or Others (UPIRTSO)

Any unanticipated problem or adverse event that meets the following three criteria:

- **Serious:** Serious problems or events that results in significant harm, (which may be physical, psychological, financial, social, economic, or legal) or increased risk for the subject or others (including individuals who are not research subjects). These include: (1) death; (2) life threatening adverse experience; (3) hospitalization - inpatient, new, or prolonged; (4) disability/incapacity - persistent or significant; (5) birth defect/anomaly; (6) breach of confidentiality and (7) other problems, events, or new information (i.e. publications, DSMB reports, interim findings, product labeling change) that in the opinion of the local investigator may adversely affect the rights, safety, or welfare of the subjects or others, or substantially compromise the research data, **AND**
- **Unanticipated:** (i.e. unexpected) problems or events are those that are not already described as potential risks in the protocol, consent document, not listed in the Investigator's Brochure, or not part of an underlying disease. A problem or event is "unanticipated" when it was unforeseeable at the time of its occurrence. A problem or event is "unanticipated" when it occurs at an increased frequency or at an increased severity than expected, **AND**
- **Related:** A problem or event is "related" if it is possibly related to the research procedures.

Adverse Event

An untoward or undesirable experience associated with the use of a medical product (i.e. drug, device, biologic) in a patient or research subject.

Serious Adverse Event

Adverse events are classified as serious or non-serious. Serious problems/events can be well defined and include;

- death
- life threatening adverse experience
- hospitalization
- inpatient, new, or prolonged; disability/incapacity
- persistent or significant disability or incapacity
- birth defect/anomaly

and/or per protocol may be problems/events that in the opinion of the sponsor-investigator may have adversely affected the rights, safety, or welfare of the subjects or others, or substantially compromised the research data.

All adverse events that do not meet any of the criteria for serious, should be regarded as **non-serious adverse events**.

Adverse Event Reporting Period

For this study, the study treatment follow-up period is defined as 30 days following the last administration of study treatment.

Preexisting Condition

A preexisting condition is one that is present at the start of the study. A preexisting condition should be recorded as an adverse event if the frequency, intensity, or the character of the condition worsens during the study period.

General Physical Examination Findings

At screening, any clinically significant abnormality should be recorded as a preexisting condition. At the end of the study, any new clinically significant findings/abnormalities that meet the definition of an adverse event must also be recorded and documented as an adverse event.

A thorough baseline screening will be followed for all subjects and is outlined in [Table-2](#). A detailed list of the methods in which baseline screening will be performed is outlined in [Supplemental 2](#). All blood draws and safety assessments must be performed **prior** to study treatment administration. Appropriate safety assessments (e.g., evaluation of AEs and SAEs) should be repeated after dosing with study treatment. A physical examination, including general appearance and vital signs, will be performed as indicated in [Table-2](#). If indicated, based on medical history and/or symptoms, additional exams will be performed at the discretion of the investigator. If possible, the same member of the study site staff throughout the study will perform assessments for an individual subject. Information for all physical examinations will be included in the source documentation at the study site. Significant findings that are present prior to the subject signing informed consent will be included in the Medical History. Significant findings made after the signing of the informed consent, which meet the definition of an AE, must be recorded as an AE. Vital signs (blood pressure, pulse, height, weight) will be assessed at each physical examination as indicated in [Table-2](#) (see [Supplemental 2](#) for details on how to acquire vital signs). Whether action needs to be taken to address notable vital signs will be decided by the investigator, considering the overall status of the subject.

Supplemental 1: Appropriateness of Measures

Skin Scoring:

There are no validated skin scoring systems for LP. Therefore, we will use simple measures of BSA which is objective and PGA which is well validated in other inflammatory skin conditions. Additionally, we will simply annotate the number of lesions on the individual as a marker of total disease burden. The later measure, CAILS was devised for evaluation of cutaneous T-cell lymphoma lesions for trial purposes. This system provides accurate measurements of CTCL patches, plaques, and tumors. This scoring system captures lesion redness, size, texture,

pigmentation and elevation characteristics. We will use a Modified CAILS scoring system that discards pigmentation scoring as resolving LP lesions inherently leave behind hyperpigmented skin changes which may confound active lesion scoring. This will provide a composite analysis of the index lesions as well as the general body involvement of the individual. The Modified CAILS system is advantageous over the PASI or EASI system in that it allows for more accurate calculation of surface area and incorporates that into the final score.

In cases where some or all of the affected body regions contain such extensive LP disease that make counting individual LP lesions unfeasible, the lesion count in these areas will be estimated. The palmar surface of the hand equates to approximately 1% BSA. To estimate the lesion count in a body region of extensive disease, the number of lesions counted within an area equivalent to the palmar surface of the hand within that extensively diseased body region will be multiplied by the representative BSA of that body region to determine the estimated lesion count contained in that body region. Representative BSAs of body regions are defined as follows: head (7%), neck (2%), anterior trunk (13%), arms (8%), forearms (6%), hands (5%), posterior trunk (13%), buttocks (5%), thighs (19%), legs (14%), feet (7%) and groin (1%).

Itch Scoring:

The NRS and Skindex-16 are all well validated measures of itch. The first score measure focuses in upon a gestalt of itch. The later scoring system focuses in upon the itch and its impact upon quality of life.

Supplemental 2: Safety Measures

Baseline Screening:

A serum β -hCG test will be performed in all pre-menopausal women as indicated. All pre-menopausal women who are not sterile at screening will also have a urine pregnancy test performed locally as indicated. Any woman with a confirmed positive pregnancy test during screening is not eligible for the study. A positive urine pregnancy test during the treatment periods of the study requires immediate interruption of study treatment until serum β -hCG is performed and found to be negative. If the serum β -hCG test is positive, study treatment must be definitively discontinued.

Blood Pressure and Pulse:

Height and Weight:

Height and body weight will be measured in indoor clothing, but without shoes. If possible, body weight assessments should be performed by the same study site staff member and using the same scale throughout the study.

Blood Draws:

Subjects should avoid smoking within the hour preceding the blood draws. All laboratory studies will be conducted within the Mayo Clinic Health Systems (Mayo Clinic Arizona and Mayo Clinic Rochester). Details on the collections, shipment of samples and reporting of results will follow

Mayo Clinic's current protocols. For the identification of notable values, the Mayo Clinic reference laboratory should be consulted.

Supplemental 3: Safety Monitoring

Infection monitoring:

Study subjects will be evaluated at each visit for signs or symptoms of infection.

- Vitals signs as well as constitutional symptoms will be assessed.
- Assessment for common infections such as cellulitis as well as oral, vaginal, and cutaneous candidiasis will be performed

Post-study Adverse Event

All unresolved adverse events should be followed by the sponsor-investigator until the events are resolved, the subject is lost to follow-up, or the adverse event is otherwise explained. At the last scheduled visit, the sponsor-investigator should instruct each subject to report, to the sponsor-investigator, any subsequent event(s) that the subject, or the subject's personal physician, believes might reasonably be related to participation in this study.

Abnormal Laboratory Values

A clinical laboratory abnormality should be documented as an adverse event if

- they induce clinical signs or symptoms,
- they are considered clinically significant,
- they require therapy.

Laboratory studies will be drawn as indicated in Table-2. Whether action needs to be taken to address notable laboratory values will be decided by the investigator, considering the overall status of the subject. Hematology assessments will be measured at all scheduled study visits specified in Table-2. Serum chemistry will be a comprehensive metabolic panel will be measured at all scheduled study visits specified in Table-2.

Hospitalization, Prolonged Hospitalization or Surgery

Any adverse event that results in hospitalization or prolonged hospitalization should be documented and reported as a serious adverse event unless specifically instructed otherwise in this protocol. Any condition responsible for surgery should be documented as an adverse event if the condition meets the criteria for an adverse event.

Neither the condition, hospitalization, prolonged hospitalization, nor surgery are reported as an adverse event in the following circumstances:

- Hospitalization or prolonged hospitalization for diagnostic or elective surgical procedures for a preexisting condition. Surgery should **not** be reported as an outcome of an adverse event if the purpose of the surgery was elective or diagnostic and the outcome was uneventful.

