INCB018424 taken systemically can inhibit the growth of blood cells. Low blood cells can make subjects more susceptible to infections by bacteria, virus, and fungi. The risk is low with systemic therapy and was not noted with topical therapy but subjects will be monitored for any signs of inhibition of their blood counts.

Infection risk:

There is a theoretical increase in risk of infection with topical use of INCB018424 PHOSPHATE CREAM. This will be monitored for.

INCB018424 may increase risk of infections and reactivation of latent infections such as Tuberculosis or Valley Fever. Serious bacterial, fungal and viral infections were observed in patients receiving INCB018424. Please seek medical advice if signs or symptoms suggestive of infection occur.

Allergy:

It is possible that some people could have an allergic reaction to INCB018424 PHOSPHATE CREAM.

Cancer Risk:

INCB018424 PHOSPHATE CREAM may have the potential to affect subject's immune system; they may be at increased risk for infections and possibly cancer. Live vaccines should not be given concurrently with INCB018424 PHOSPHATE CREAM.

Pregnancy Risk:

The effect of the study drug on a fetus (developing baby still in the womb), or on a breastfeeding infant, is unknown and may be harmful. Because of these risks, women cannot take part in this study if they are pregnant or breastfeeding.

Skin biopsy:

A skin biopsy is generally a safe procedure, but some potential risks may include local pain, mild local bruising, bleeding, scarring, and an infection at the site where the skin biopsy was performed. If a topical antibiotic is used afterwards, then there is a small risk of an allergic reaction.

Chest X-ray:

Subjects will be exposed to radiation from the chest x-ray. The amount of radiation has a low risk of harmful effects.

Blood draw:

The risks of drawing blood include pain, bruising, lightheadedness, and/or fainting, or rarely, infection at the site of the needle stick.

Other:

As with all research, there is a chance that confidentiality could be compromised; however, we take precautions to minimize this risk.

3 Study Objectives

Primary Objective:

To determine the efficacy of INCB018424 PHOSPHATE CREAM as measured by the change in Modified CAILS score of the index treatment and control lesion (weeks 0 and 4) and changes in lesion count (week 0 and 4)

Secondary Objective:

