4.4 Primary Study Endpoints

Change in Modified CAILS of index treatment lesion and index control lesion (week 0 and 4) and change in lesion count (week 0 and week 4).

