5.1 Inclusion Criteria

Subjects eligible for inclusion in this study must fulfill **all** the following criteria:

- Subjects must be able to understand and comply with the requirements of the study and communicate with the investigator. Subjects must give written, signed, and dated informed consent before any study related activity is performed. When appropriate, a legal representative will sign the informed consent according to local laws and regulation
- Both men and women must be at least 18 years of age at the time of screening
- Subjects must have clinical and histological features of LP
- LP up to 20% of the BSA
- Subjects must have a minimum of 4 lesions, ideally 10 lesions of LP
- Subjects must have treatment naïve cutaneous LP or treatment refractory disease, as defined by failure of at least one established treatment for LP
 - Failure of prior therapy
 - Topical treatment
 - Systemic immunosuppressant
 - Oral metronidazole
 - Oral sulfasalazine
 - Oral retinoid

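### Where lesions cannot be counted, one palm's count is multiplied by the whole region's BSA share, so a partly affected region can be overcounted (up to 2.0-fold for one leg) and the week 0 to 4 change distorted

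*Combined protocol and SAP*

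**What the plan says.** Supplemental 1 (Skin Scoring), placed within Section 9.1, covers regions where extensive disease would "make counting individual LP lesions unfeasible, the lesion count in these areas will be estimated". It takes "the number of lesions counted within an area equivalent to the palmar surface of the hand within that extensively diseased body region" and states that "The palmar surface of the hand equates to approximately 1% BSA". That count "will be multiplied by the representative BSA of that body region to determine the estimated lesion count contained in that body region". Twelve fixed regional shares follow; legs are 14% and thighs 19%.

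The rule does not say where in the region the palm goes. It has no term for how much of the region is affected and no separate share for one side. It does not require the same method at later visits.

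Lesion count matters because Section 3 (Primary Objective) and Section 4.4 both make its change from week 0 to week 4 part of the primary efficacy assessment, alongside Modified CAILS. Neither says whether the change is absolute or percent. Section 5.1 admits "LP up to 20% of the BSA". Section 8.2 summarises continuous outcomes by mean and SD or by median and range, uses Wilcoxon tests, and does not mention estimated counts.

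**The concern.** Scaling a one-palm count by a whole region's area gives the right total only if the sampled density holds over the whole region. A subject with one affected leg, or with disease over part of a region, does not meet that condition.

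An error of constant proportion would cancel from a percent change. This one need not be constant. It depends on how much of the region is affected, which treatment is meant to change. It also disappears once a region becomes countable, which treatment may bring about. The recorded week 0 to 4 change can therefore be too small or too large. Lesion count has no untreated comparator to reveal this, because the control lesion serves Modified CAILS only. Section 8.2 intends the resulting effect sizes for planning later studies.

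**Working it through.** **Inputs from the documents.** One palm is about 1% BSA. The regional shares, from largest to smallest, are thighs 19, legs 14, anterior and posterior trunk 13 each, arms 8, head and feet 7 each, forearms 6, hands and buttocks 5 each, neck 2 and groin 1.

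Sum: 19+14+13+13+8+7+7+6+5+5+2+1 = 100. The shares cover the whole body, so legs (14) must mean both legs, and one leg is 14/2 = 7 palm-areas. The text does not say this; it follows from the total.

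**Assumptions (not in the documents).** There are c = 20 lesions per affected palm-area; c cancels from the ratios. A is the number of affected palm-areas. The palm lies on affected skin, and density there is uniform.

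**Size of the overcount.** The rule gives c × R. If the rest of the region is clear, the true count is c × A, so the ratio is R/A. For legs (R = 14) the rule always gives 20 × 14 = 280.

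| Situation | True count | Recorded / true |
|---|---|---|
| Both legs evenly involved | 20 × 14 = 280 | 1.0 |
| One leg full, other leg at half density | 20 × 7 + 10 × 7 = 210 | 1.33 |
| One leg full, other leg at one fifth density | 20 × 7 + 4 × 7 = 168 | 1.67 |
| 10 of 14 palm-areas affected, rest clear | 20 × 10 = 200 | 1.4 |
| One leg full, other leg clear | 20 × 7 = 140 | 2.0 |

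If the palm were instead placed at random over both legs, with one leg affected, its expected count would be 140/14 = 10. The estimate would then average 10 × 14 = 140, which is unbiased.

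**Effect on the week 0 to 4 change.**

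1. *Estimated twice, area fixed, density halves (one leg).* True 140 to 70; recorded 280 to 10 × 14 = 140. The percent fall is right (50%), but the absolute fall is recorded as 140 instead of 70.
2. *Estimated twice, patch contracts from A = 10 to 7 at constant density.* True 200 to 140, a fall of 1 − 140/200 = 30%. Recorded 280 to 280, no change.
3. *Estimated at week 0, countable at week 4 after a true halving (one leg).* True 140 to 70, a 50% fall. Recorded 280 to 70, a fall of 1 − 70/280 = 75%.

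**With A in place of R.** Case 1 becomes 20 × 7 = 140 to 10 × 7 = 70. Case 2 becomes 200 to 140. Case 3 becomes 140 to 70. Each matches the true change.

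**The case against.** The strongest reply is that the bias is conditional. Supplemental 1 places the palm within the diseased region, not expressly on affected skin, and random placement would be unbiased on average. R/A also needs the rest of the region to be clear. Both points stand, so R/A is an upper figure. Sampling affected skin remains the natural reading, and nothing in the text calls for random placement.

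A second reply is that the rule will rarely apply. Section 5.1 requires only 4 lesions, ideally 10. Section 4.1 has all lesions annotated, photographed, scored and circled, so a direct count should often exist. This also stands: the documents do not show how many of the 12 subjects would need an estimate. They also do not tell assessors to recount from photographs, and those records do not correct the multiplier.

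A third reply is that the consequences are contained. Medians and Wilcoxon tests limit one subject's influence, Section 8.2 describes the study as for estimation only, and BSA is assessed separately, so a contraction missed by lesion count should appear there. This is right, and it lowers the importance of the point.

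A reader might infer stronger claims, such as overcounts far above 2, or a halving of the affected area from 8 to 4 palm-areas recorded as no change (14/4 = 3.5 at week 4). Those need disease confined to a small part of a region, which fits poorly with a rule reserved for disease too extensive to count. A false rise from counting at week 0 and estimating at week 4 would need unchanged or improved disease to become uncountable, which is implausible.

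**Conclusion.** The rule as written is wrong for a partly affected region when the palm is placed on affected skin. For legs the overcount is at most 2.0-fold with one leg fully affected and the other clear, 1.33-fold with the other leg at half density, and nil when the region is evenly involved. With the same method and the same area at both visits, percent change is unaffected and only absolute change is inflated. A contracting patch can hide a true 30% fall, and a switch from estimate to count can turn a true 50% fall into a recorded 75% fall. The regional shares come from the document; the densities and affected areas are illustrative.

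The point is minor. Modified CAILS and BSA are not affected, and the rule may seldom be used. A reader might infer that the lesion-count result as a whole is unreliable; the documents do not support that, because directly counted regions are untouched. Nor does the 20% BSA entry limit prove that an overcount must occur. It limits lesional skin, not the area over which lesions are scattered.

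**What to change.** In Supplemental 1, replace the region's full share as multiplier with the number of palm-areas, in that region and on that side, over which lesions are distributed at that visit. Record that area and a counted/estimated flag for each region at weeks 0 and 4. Keep a direct count wherever one is feasible. Where the method differs between the two visits, also report the change using the same method at both, as a sensitivity analysis, where the data allow.

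The cost is a wording change, an area field and a flag on the CRF, and a few minutes for subjects with extensive regions. It adds a small judgement about the affected area. Sampling noise remains in any estimate: for 140 lesions spread at random over 7 palm-areas, one palm gives a standard error of 7 × √(140 × 1/7 × 6/7) = 29 lesions, or 29/140 = 21%. That is the reason to prefer a direct count.

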4.1 General Description

This is a single center, exploratory, open-label, single-arm design study of 12 patients. Treatment naïve and treatment refractory patients with LP will be treated with INCB018424 PHOSPHATE CREAM. Patients who are non-responders, to physician choice standard of care, will undergo a washout period and will be enrolled in the study.

Multiple safety studies have been conducted with INCB018424 PHOSPHATE CREAM (see Safety) and a dose of 1.5% cream BID on up to 20% BSA is deemed safe. (Investigator's Brochure) The Within each cohort, the maximum reduction from baseline in the total psoriasis lesion assessment scores for the treated lesions was observed at the end of treatment (Day 28). (Investigator's Brochure) Therefore, we propose a single center, exploratory, open-label, single-arm design study of 12 patients. Treatment naïve and treatment refractory patients with LP will be treated with INCB018424 PHOSPHATE CREAM.

Individuals with LP involving less than 20% of the BSA will be eligible. Individuals must have 4 lesions at baseline, however, a minimum of 10 lesions is ideal, which are at least 5mm in diameter. 10 lesions are ideal as 2 lesions will be index lesions and 8 or more lesions will be selected from as responsive or non-responsive at 4 weeks. All lesions except for one index lesion will be treated and all lesions will be annotated, photographed, and scored. The rationale for a minimum of 8 lesions is based upon the assumption of a 50% response rate at 2 weeks. With 8 lesions, there would be a less than 1% chance that all 8 lesions would respond. Ideally, the 2 index lesions will be 10mm in diameter but this is not a requirement. Prior treatment will be allowed; however, a washout period of 2 weeks for topical and 4 weeks for systemic agents is required. At the washout period, individuals will undergo evaluation with a PGA, BSA calculation, and have the 2 largest, representative lesions selected for evaluation using a modified CAILS score lesion A- treatment index lesion and B-index control lesion. The determination of which lesion receives treatment and which is a control will be determined randomly. The additional lesions will be photographed, measured, scored, and recorded with Modified CAILS scores as well. The later calculations will be used for the determination of responsive and non-responsive lesions. Additional Pruritus measures using the NRS and Skindex-16 will be collected at that time.

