4.3 Duration of Participation

The study consists of 3 epochs: screening/washout period (of at least 1 week and up to 4 weeks), treatment epoch (of 8 weeks from screen/washout), and follow up epoch (of 4 weeks). The screening and washout period will allow for treatment naïve/ new diagnosis LP to undergo evaluation and diagnosis and for treatment refractory to undergo a washout. The total duration of the study will be 13-16 weeks.

Tables:

• **Table-1: Prohibited treatment**

Prohibited treatments^{†, ‡}	Washout period (before Randomization Visit)
Any concomitant oral or topical JAK inhibitor	Prohibited
Any biologic drug	Stable dose for 3 months
Immunomodulation treatments for LP [§] [e.g., methotrexate, cyclosporine A, corticosteroids (oral, i.v., intramuscular, s.c., intra-articular, transdermal), mycophenolate mofetil, azathioprine]	4 weeks
Topical treatment that is likely to impact signs and symptoms of LP (e.g., pimecrolimus, tacrolimus)	2 weeks
Non-immunosuppressive agents (tetracycline antibiotics & niacinamide)	2 weeks
Prohibited regimen of Topical Corticosteroids (TCS)	
TCS on any location on body (including face, scalp and/or genitoanal area)	2 weeks

[†] If the prohibited treatment is being used during the study for any indication, the subject must discontinue use of the prohibited treatment if he/she wishes to continue in the study.

[‡] In case of undue safety risk for the subject, the subject should discontinue study treatment at the discretion of the investigator/qualified site staff. If the subject received a live virus vaccination during the study, the subject must discontinue study treatment.

[§]Inhalative CS with only a topical effect (e.g., to treat asthma) are not considered “systemic immunomodulation treatments” and are therefore acceptable as co-medication. Immunosuppressive medication for conditions other than LP will be allowed.

Table-2: Screening and Visits (+/- 2 day window)

	Screening	Day 0	Week 1	Week 2	Week 3	Week 4	Week 8	Week 12

INCB18424		X	X	X	X	X		
Physical Exam	X	X	X	X	X	X	X	X
Adverse Event Assessment		X	X	X	X	X	X	X
Chest X-ray	X							
Assessments: PGA, BSA, lesional number, Modified CAILS, Skindex-16, Pruritus NRS		X	X	X	X	X	X	X
Photographer		X	X	X	X	X	X	X
Skin Biopsy (tissue/serum bank)		X				X		
Urine Pregnancy Test	X							
Venipuncture	X	X	X	X	X	X	X	X
Biomarker/RNAseq blood (tissue/serum bank)		X		X		X		
CMP	X		X	X	X	X	X	X
CBC	X		X	X	X	X	X	X
Quantiferon Gold	X							
Hepatitis B	X							
Hepatitis C	X							

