6.2 Treatment Regimen

Subjects will apply the study drug topically to LP lesions twice daily. Treatment will take place from Day 0 to Week 8.

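### The only pregnancy test on the visit schedule is the screening urine test, up to 4 weeks before the first dose; none is scheduled on Day 0 or during treatment

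*Combined protocol and SAP*

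**What the plan says.** Section 4.3 describes a "screening/washout period (of at least 1 week and up to 4 weeks"), then 8 weeks of treatment and 4 weeks of follow-up, and adds: "The total duration of the study will be 13-16 weeks". Section 6.2 says "Treatment will take place from Day 0 to Week 8".

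In Table-2 (section 4.3) the row "Urine Pregnancy Test" is marked in the Screening column only. The CMP and CBC rows of the same table are marked at Screening and from Week 1 through Week 12. Section 7.1 lists the urine test at the screening visit, for women able to become pregnant. The lists in sections 7.2 to 7.8 contain no pregnancy test.

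Supplemental 2, Baseline Screening (printed within section 9.1), says that a serum beta-hCG "test will be performed in all pre-menopausal women as indicated". Neither Table-2 nor section 7 assigns that test a visit. The same paragraph sets the on-treatment rule: "A positive urine pregnancy test during the treatment periods of the study requires immediate interruption of study treatment" until a serum beta-hCG "is performed and found to be negative". If the serum test is positive, treatment stops for good.

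Section 5.2 excludes pregnant and nursing women but admits women of childbearing potential on basic contraception, which includes a condom or occlusive cap. The Pregnancy Risk paragraph of section 2.6 calls the effect on a fetus unknown and possibly harmful.

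**The concern.** The plan says what to do with a positive test during treatment but schedules no test that could produce one. It also excludes pregnancy without checking for it at the point where exposure begins. A woman who conceives during screening/washout, or whose pregnancy was too early to detect at screening, could start the cream and continue until pregnancy is suspected on other grounds, even if the site follows the schedule exactly.

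At stake is avoidable fetal exposure. Section 2.3 reports increased postimplantation loss at the higher doses in the rat fertility and early embryonic study. No efficacy endpoint, estimate or analysis depends on this point.

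**Working it through.** **Inputs.** Screening/washout epoch w = 1 to 4 weeks, treatment 8 weeks, follow-up 4 weeks, visit window ±2 days (section 4.3 and Table-2); dosing from Day 0 to Week 8 (section 6.2); 12 subjects (section 4.2). The day of the screening test within the epoch is not given. Let d be the number of weeks into the epoch at which it is done.

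**The plan's own figure.** Shortest: 1 + 8 + 4 = 13 weeks. Longest: 4 + 8 + 4 = 16 weeks. Both match the stated duration.

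**Gaps from the screening test.** To first dose: w − d. To last dose: w − d + 8.

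| Case | To first dose | To last dose |
|---|---|---|
| w = 4, d = 0 | 4 weeks | 4 + 8 = 12 weeks |
| w = 1, d = 0 | 1 week | 1 + 8 = 9 weeks |
| tested just before Day 0 (d close to w) | about 0 | about 8 weeks |

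**Longest interval from a scheduled test to a dose**, taking w = 4, d = 0 and allowing the window:

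- As written: 28 + 56 + 2 = 86 days.
- With a Day 0 test: 56 + 2 = 58 days.
- With Day 0 and Week 4 tests: the larger of 28 + 2 = 30 and (56 + 2) − (28 − 2) = 32, so 32 days.

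**Why Week 4 is the second point.** Visits on treatment fall at Day 0 and Weeks 1, 2, 3, 4 and 8. The intervals are 1, 1, 1, 1 and 4 weeks, so the longest one follows the Week 4 dispensing.

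**Does other text fill the gap?**

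- *As-indicated testing in Supplemental 2.* If the phrase points to Table-2, as similar wording does in section 4.6, testing is at screening only. If it means clinically indicated, testing is discretionary. Neither reading schedules a test on Day 0 or later.
- *Additional exams (sections 4.6 and 9.1).* These follow from history or symptoms, at the investigator's discretion.
- *Blood samples at each visit (section 7).* The laboratory rows of Table-2 include no hCG.
- *Pregnancy reporting (sections 9.3.2 and 9.5).* The time limits run from learning of a pregnancy, so they do not detect one. Section 9.3.2 gives steps for a positive baseline test but schedules none on Day 0.

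**Number of tests added.** At most 1 × 12 = 12 for Day 0, or 2 × 12 = 24 with Week 4. The number of women of childbearing potential is not given and could be anywhere from 0 to 12.

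**The case against.** The interruption rule is conditional, so a for-cause test satisfies it, and the protocol allows such tests. Nothing in the documents requires testing on Day 0 or during treatment. That stands: the rule is usable as written, and this is a gap in the schedule, not a contradiction.

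The visit lists in section 7 are weak corroboration. They are lay summaries that leave out PGA, BSA, Skindex-16, CBC and CMP, all of which Table-2 schedules. That also stands; the evidence is mainly the Table-2 row, together with section 7.1.

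The risk is small. Contraception is required and subjects are asked about health problems at every visit from Day 0. The drug was not teratogenic in rat or rabbit, and the prenatal and postnatal rat study had no adverse findings for embryo-fetal survival (section 2.3). Mean topical bioavailability was about 3 to 5% (section 6.1). This justifies a minor rating but does not replace a test. Early pregnancy may produce no complaint, and exposure is not nil: mean plasma concentration was 60.99 ± 73.85 nM in the cohort treated over 14 to 20% BSA (section 6.1), and this trial allows up to 20%.

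A reader might infer fixed gaps by patient type, because section 4.1 states that "a washout period of 2 weeks for topical and 4 weeks for systemic agents is required": 2 and 10 weeks after topical therapy, 4 and 12 after systemic therapy. The documents do not support that. Those figures assume washout starts at screening. Table-1 counts washout back from the randomization visit, and the epoch minimum is 1 week for everyone, so a patient who stopped therapy before screening could have the shortest epoch.

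**Conclusion.** The point holds as a minor, patient-safety improvement. No pregnancy test is scheduled after screening. The gap is up to 4 weeks to the first dose and up to 12 weeks to the last, both resting on the assumption that the test is done on the first day of the longest epoch. At the shortest epoch they are 1 and 9 weeks, and a later test shortens them towards 0 and 8.

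Two stronger readings should be resisted. A reader might infer that the urine test is the only pregnancy test the protocol names; it is not, since Supplemental 2 names a serum test, though without a visit. A reader might also infer that the protocol has no plan for pregnancy on treatment; it has rules for interruption, serum confirmation, discontinuation, reporting and follow-up. What is missing is a scheduled test to set them in motion.

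The case for Day 0 is the firmer one, because section 4.6 already wants safety assessments done before study treatment. Week 4 is a sensible choice of interval, not something the text demands.

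**What to change.** **Priority.** For women of childbearing potential, add a urine pregnancy test at Day 0 to Table-2 and section 7.2, done before the biopsies and the first application. If it is positive, do not start treatment; confirm by serum beta-hCG and treat a confirmed positive as ineligible. Add one line to Supplemental 2 to say so, because its present rules cover positives during screening and during treatment, and a pre-dose Day 0 result is not clearly either.

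**Secondary.** Add a urine test at Week 4 to Table-2 and section 7.6, before drug is dispensed for weeks 4 to 8, and apply the existing interruption and confirmation rule.

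**Cost.** At most 12 urine tests, or 24 with Week 4, at existing visits and with no new staff. The change needs a small protocol amendment submitted to the IRB. A woman who tests positive on Day 0 may be lost from the 12. She would have received no dose and so would fall outside the section 8.3 population. Section 5.4.1 says withdrawn subjects are not replaced, so the amendment should state whether a subject excluded before dosing may be.
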